8.4.2 UNANTICIPATED PROBLEMS REPORTING

The Moscow site investigator will report unanticipated problems (UPs) to the IRB of the PRIZMA Research Center (FWA00017140), to the Scientific and Educational Center in Moscow IRB#1 (00010190), and to the principal investigator (PI). The PI will submit the report to the IRB of the University of Illinois at Chicago (IRB #00009693). The UP report will include the following information:

- Protocol identifying information: protocol title and number, PI’s name, and the IRB project number
- A detailed description of the event, incident, experience, or outcome
- An explanation of the basis for determining that the event, incident, experience, or outcome represents an UP
- A description of any changes to the protocol or other corrective actions that have been taken or are proposed in response to the UP

To satisfy the requirement for prompt reporting, UPs will be reported using the following timeline:

- UPs that are serious adverse events (SAEs) will be reported to NIDA and to the three IRBs within 3 days of the investigator becoming aware of the event
- Any other UP will be reported to the three IRBs and to NIDA within 10 days of the investigator becoming aware of the problem
- The UIC Office for the Protection of Research Subjects (OPRS) will promptly report to applicable institutional officials, funding sources, agency heads and regulatory agencies determinations by the IRB that an event represents a reportable unanticipated problem involving risks to subjects or others as determined by the IRB. The letter from the OPRS Director will be sent to the Office for Human Research Protections (OHRP) within 10 working days of the convened IRB’s determination.

In the event a situation requires extended time to investigate or resolve, a preliminary report will be sent and followed by a final report. In no event will a preliminary report to institutional officials, the supporting agency head, or OHRP be delayed beyond 30 days of the OPRS/IRB receiving notice of a reportable event.

8.4.3 REPORTING UNANTICIPATED PROBLEMS TO PARTICIPANTS

N/A

9 STATISTICAL CONSIDERATIONS

9.1 STATISTICAL HYPOTHESES

- Primary Endpoints:

We hypothesize that, compared to MWID who receive a health education control intervention, those who receive the MASLIHAT peer education intervention will have reduced frequency of syringe and other injection equipment sharing, and reduced frequency of vaginal and anal intercourse without a condom 12 months following the intervention. Alternatively, our null hypothesis is that there will be no difference in the effects of MASLIHAT and the health education control intervention on injection and sexual risk behavior of intervention participants 12 months following the intervention.

We hypothesize that, compared to IDU network members of MWID who receive a health education control intervention, IDU network members of MWID who receive the MASLIHAT peer education intervention will have reduced frequency of syringe and other injection equipment sharing, and reduced frequency of vaginal and anal intercourse without a condom 12 months following the intervention. Alternatively, our null hypothesis is that there will be no difference in the effects of MASLIHAT and the health education control intervention on injection and sexual risk behavior of IDU network members 12 months following the intervention.

- Secondary Endpoint(s):

We hypothesize that, compared to MWID who receive a health education control intervention, those who receive the MASLIHAT peer education intervention will have lower incidence of HIV infection and lower incidence of hepatitis C infection 12 months following the intervention. Alternatively, our null hypothesis is that there will be no difference in the effects of MASLIHAT and the health education control intervention on the incidence of HIV or HCV among intervention participants 12 months following the intervention.

We hypothesize that, compared to IDU network members of MWID who receive a health education control intervention, IDU network members of MWID who receive the MASLIHAT peer education intervention will have lower incidence of HIV infection and lower incidence of hepatitis C infection 12

months following the intervention. Alternatively, our null hypothesis is that there will be no difference in the effects of MASLIHAT and the health education control intervention on the incidence of HIV or HCV among IDU network members 12 months following the intervention.

Statistical Analysis Plan (SAP): A formal SAP will be prepared prior to the first interim analysis of 3-month follow-up outcomes.

9.2 SAMPLE SIZE DETERMINATION

We estimated power allowing up to 10% attrition among intervention participants and up to 15% attrition among network members. Power calculations were computed using PASS software and considering effects observed in the pilot study.

We expect to see large reductions in syringe sharing and condomless sex in the MASLIHAT intervention group, and little change in these behaviors in the control group. In the pilot study, syringe sharing decreased from 52% at baseline to 0% at six months, and condomless sex decreased from 35% at baseline to 1% at six months. For binary outcomes, we computed Mixed Models Tests for Two Proportions in a 3-Level Hierarchical Design (Level-3 Randomization), with an intracluster correlation of 0.05 and alpha=.01. We computed power for outcomes ranging from 0.30 to 0.50 for the control group, and 0.05 to 0.15 for the MASLIHAT intervention group, and with 10, 20 or 30 subjects per cluster, representing intervention participants, network members, and the complete sample. We will have at least 80% power to detect predicted changes in condomless sex, and over 90% power to detect predicted changes in syringe sharing. In the larger sample, we will have adequate power to detect effects even if they are not as large as anticipated.

The intervention also targets alcohol use and in the pilot study, days of alcohol use in the past month decreased from 5 to 2, with $b/SE = -6.52$, yielding a Cohen's d effect size of -0.69. We estimated power by computing Mixed Models Tests for the Slope Difference in a 3-Level Hierarchical Design with Fixed Slopes (Level-3 Randomization), with subject $icc=0.30$ and $alpha=0.01$, for a standardized mean difference (SMD) of 0.50 to 0.70, with cluster sizes of 10, 20. and 30. For the intervention participants, we will have at least 80% power to detect a $SMD=0.70$; for network members we will have at least 80% power to detect a $SMD=0.50$, and for the complete sample we will have at least 80% power to detect a $SMD=0.41$.

For HIV and hepatitis C virus (HCV) outcomes, we computed detectable effects for a one-sided Test for the Difference between Two Poisson Rates in a Cluster-Randomized Design, given our sample with $k=30$ subjects per cluster, coefficient of variation (CV) = 0.50 for the control group and CV=1 for the intervention group, $alpha=0.05$, and $power=0.80$. Assuming a base rate HIV incidence of 10% for the control group, we will have at least 80% power to detect an event rate ratio of 0.11, corresponding to an incidence rate of 1% in the treatment group. For HCV, we must assume that a fair number of the sample will be infected as baseline and therefore excluded from the analysis. Assuming 15 subjects per cluster and HCV base rate incidence of 40%, we will have at least 80% power to detect an event rate ratio of 0.21, corresponding to an incidence rate of 8.6% in the treatment group.

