9.4 STATISTICAL ANALYSES

9.4.1 GENERAL APPROACH

Descriptive analyses of the study sample will include percentages for categorical variables and means and standard deviations for continuous measures. Chi-square tests and t-tests will be computed to compare study arms on baseline sociodemographic measures. We will compare follow-up between conditions using GEE logistic regression. Results will be reported as odds ratios with 95% confidence intervals and exact p-values for 2-tailed tests.

We will examine the distributions of outcome measures to ascertain whether there is sufficient variability to analyze frequency measures as ordinal. Response categories with a small number of responses will be collapsed for analysis. We will analyze missing data patterns to assess the extent of missing data, and to determine if there is evidence of non-ignorable missingness (i.e. missing not at random, MNAR).

We will conduct repeated measures linear, logistic, and modified Poisson regressions using mixed effects models with random intercepts for subject and recruitment site to test the effect of intervention condition on changes in mediator and outcome variables. In the event of missing data in more than 5% of cases, or unbalanced loss-to-follow-up, analyses will be conducted in Mplus using full-information maximum likelihood methods. We will include the interaction of time and participant type (intervention participant vs. network member) to test for differential effects. Following analysis of the main outcomes we will conduct analyses to explore hypothesized mediation and moderation effects.

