9.4.2 ANALYSIS OF THE PRIMARY ENDPOINT(S)

Relative frequency of syringe sharing, equipment sharing, and vaginal or anal sex without a condom in the past 3 months will be measured at each time point on a 7-point Likert-type scale (Never, Rarely, Less than half the time, About half the time, More than half the time, Most of the time, Always). We will analyze ordinal outcomes, and we will also dichotomize responses to analyze binary (none/any) outcomes.

We will conduct repeated measures mixed effects regressions with random intercepts for subject and recruitment site to test the effect of intervention condition on changes in the outcome variables. We will use ordinal logistic regression for ordinal outcomes and modified Poisson regression for binary outcomes. We will conduct a test of the proportional odds assumption with a likelihood ratio test comparing the proportional odds model with a non-proportional odds model.⁷⁴ We will include the interaction of time and participant type (intervention participant vs. network member) to test for differential effects. If the interaction term suggests differential effects ($p < .10$), we will stratify analyses by participant type. Sociodemographic characteristics (age, education, time in Moscow) will be included as covariates in the analysis if they are related to the outcome at baseline or if they vary significantly across conditions. All participants with at least one follow-up interview will be included in the analysis.

Dosage: If there is variability in attendance, we will estimate repeated measures mixed effect models predicting outcomes with session attendance and the interaction between time, intervention condition, and session attendance as predictors. A significant interaction effect will indicate that the effect of the intervention is moderated by session attendance.

Social Network Diffusion. Additional analyses among network members will examine associations between exposure to intervention concepts (i.e. conversations about health, drugs/alcohol HIV) and changes in outcomes over time.

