The results of mixed effects ordinal logit models will be reported as odds ratios with 95% confidence intervals, and exact p-values. Predicted probabilities will be computed from the logit model. The results of mixed effects modified Poisson regressions will be reported as relative risk ratios with 95% confidence intervals, and exact p-values. We will also report intra-class correlations for the subject and site (cluster) levels.

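### Power for the behavioural outcomes is computed at alpha 0.01, but the analysis section gives no test level, no lead test and no multiplicity rule for the treatment effect

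*Combined protocol and SAP*

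**What the plan says.** **Level used for power.** Section 9.2 computes power for the binary behaviours "with an intracluster correlation of 0.05 and alpha=.01". It uses 0.01 again for alcohol use. For HIV and HCV, the secondary outcomes, it uses 0.05 in a "one-sided Test for the Difference between Two Poisson Rates in a Cluster-Randomized Design". No reason is given for 0.01, and its sidedness is not stated.

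**Level used for analysis.** Section 9.4.1 says of the general comparisons: "Results will be reported as odds ratios with 95% confidence intervals and exact p-values for 2-tailed tests". Section 9.4.2 says the binary models "will be reported as relative risk ratios with 95% confidence intervals, and exact p-values", and describes the ordinal models in the same way with odds ratios. The only p-value threshold in 9.4.2 for choosing between primary analyses is the 0.10 rule for the interaction of time and participant type. If that rule is met, analyses are stratified by participant type; otherwise the two types stay in one model.

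**Number of tests.** Section 9.4.2 takes syringe sharing, equipment sharing and condomless sex, analyses each as ordinal, and adds "we will also dichotomize responses to analyze binary (none/any) outcomes". Section 9.1 states separate null hypotheses for index participants and for network members, both at 12 months. Section 9.4.6 adds an analysis of behavioural outcomes at every follow-up.

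**Which outcomes are primary.** The synopsis and section 3 include heavy alcohol use. Sections 6.1.1 and 8.1 name only syringe sharing and condomless sex. Section 9.1 covers injection equipment sharing and condomless sex, without alcohol.

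**What is deferred.** Section 9.1 promises a formal SAP before the first interim analysis but commits it to no test level or hierarchy.

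**The concern.** The level at which the trial was sized does not reach the section that says how the treatment effect will be assessed. A reader of 9.4 meets only the 95% interval and may use it to decide. Several behaviours, two scales and possibly two populations are then available, and nothing says which result carries the claim. A single interval excluding 1 could be presented as efficacy at an error rate well above the one behind the power statement. The 0.10 rule also makes the number of tests depend on the data, and the separate hypotheses in 9.1 are not guaranteed a separate test.

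**Working it through.** **1. Is the stated power consistent with alpha 0.01?**

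Inputs: 12 sites, 6 per arm (6.3); 10, 20 or 30 men per cluster and ICC 0.05 (9.2); control rates 0.30–0.50 and MASLIHAT rates 0.05–0.15 (9.2). The cluster sizes fit the stated attrition: 70/6 × 0.90 = 10.5 index men and 140/6 × 0.85 = 19.8 network men per site.

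Effective number per arm with m = 10: 6 × 10 / (1 + 9 × 0.05) = 60/1.45 = 41.4.

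Power = Φ[(d − 2.576 × SE₀)/SE₁], with SE₀ from the pooled rate and SE₁ from the two separate rates, two-sided 0.01.

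- 0.35 vs 0.05: SE₀ = √(2 × 0.20 × 0.80/41.4) = 0.0879; SE₁ = √((0.2275 + 0.0475)/41.4) = 0.0815; (0.30 − 0.2265)/0.0815 = 0.90; power 81.6%. Section 9.2 says: "We will have at least 80% power to detect predicted changes in condomless sex".
- 0.50 vs 0.10: SE₀ = 0.1007; SE₁ = 0.0906; (0.40 − 0.2595)/0.0906 = 1.55; power 93.9%. Section 9.2 states over 90% for syringe sharing.

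At 0.05 the same two cases give 94.1% and 98.7%. The stated power is therefore attainable at 0.01. Section 9.2 does not say which rate pairs are the predicted ones, so the pairs are my choice from its grid. Not every pair reaches 80% with 10 per cluster: 0.30 vs 0.05 gives 67%. A t reference with 10 degrees of freedom (unpooled variance) gives 69% for 0.35 vs 0.05.

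**2. How many tests?**

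- Populations pooled: 3 behaviours × 2 scales = 6.
- Populations separate: 3 × 2 scales × 2 populations = 12.

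Heavy alcohol use and the earlier time points are left out of both counts.

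**3. Chance of at least one false positive if no effect exists.**

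Independent tests: 1 − (1 − α)^k. Correlated tests: k equicorrelated normal statistics, two-sided. The correlations are assumptions; the documents give none.

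| Tests | Each read at | Correlation 0 | 0.5 | 0.7 |
|---|---|---|---|---|
| 6 | 0.05 | 26.5% | 20.7% | 16.4% |
| 12 | 0.05 | 46.0% | 31.9% | 23.2% |
| 6 | 0.01 | 5.9% | 4.9% | 3.9% |
| 12 | 0.01 | 11.4% | 8.3% | 6.0% |
| 4 (proposed lead tests) | 0.01 | 3.9% | 3.5% | 3.0% |

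The zero-correlation column is an upper value, because the ordinal and any/none versions of one item are strongly related. With the two scales correlated 0.8–0.9 and the other correlations 0–0.5, 12 tests at 0.05 give about 30–39%.

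**4. Separating the two changes in the fix.** Under independence, going from 12 tests at 0.05 (46.0%) to 12 at 0.01 gives 11.4%; going to 4 at 0.05 gives 18.5%; doing both gives 3.9%. Both the level and the count matter.

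**The case against.** The strongest reply is that this is silence and not contradiction. A reader might infer that the plan judges efficacy by 95% intervals, so that 9.2 and 9.4 flatly disagree. The documents do not support that. They say what will be reported, and a 95% interval beside an exact p-value is compatible with declaring effects only at p < 0.01. This part of the reply stands.

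A reader might also infer that the family-wise error of this trial is 23–46%. That does not follow either. It needs 12 tests, each read at 0.05. Under 9.4.2 the populations stay pooled unless the interaction gives p < 0.10, which leaves 6 tests. Section 9.4.1 makes the ordinal analysis depend on enough variability, and 6.1.1 and 8.1 list two primary behaviours, not three. In the other direction, adding alcohol use or the repeated analyses would raise the count. The number of tests is not fixed by the documents, so any single figure is conditional.

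The promised SAP is the natural place for a remedy. However, nothing in the protocol says that it will set a test level or an order of tests, so the promise defers the matter without settling it.

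**Conclusion.** The point holds as an omission. The behavioural outcomes are powered at 0.01, that level is not carried into 9.4, and no lead behaviour, scale or population is named. Even if 0.01 is the intended level, up to 12 unranked tests carry about 6–11%, so a lead set is needed in either case. If tests were read at 0.05, the range is about 16–26% (6 tests) to 23–46% (12 tests). These figures rest on two-sided tests, a common correlation of 0 to 0.7, and counts that omit alcohol use and the earlier time points. This should be corrected, and wording is enough to do it.

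**What to change.** In 9.4.2 (and in the SAP), before outcome data are seen:

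- Name four lead tests at 12 months: any/none syringe or equipment sharing, and any/none condomless sex, each in index men and in network men, as 9.1 hypothesises. Section 3 already states these endpoints as proportions.
- Take each from a pre-specified contrast that does not depend on the p < 0.10 interaction rule.
- Declare each at two-sided 0.01 with a 99% interval (family-wise error at most 1 − 0.99⁴ = 3.9%), or use Holm at 5% across the four.
- Label the ordinal analyses and the earlier time points as supportive.
- State whether heavy alcohol use is in the family. With it in both populations there are six tests, and 1 − 0.99⁶ = 5.9% at 0.01, so Holm at 5% would be needed. Otherwise list it as secondary in the synopsis and section 3.
- Reword 9.1, which hypothesises lower frequency, to match the any/none lead scale.

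**Cost.** A 99% interval is about 31% wider than a 95% one on the analysis scale (2.576/1.960 = 1.31). Stated power is unchanged under the 0.01 rule because 9.2 already used it; that is not a check of the power itself, and 9.2 names syringe sharing and not the combined sharing outcome. Holm across four starts at 0.05/4 = 0.0125, which is no stricter than 0.01. Holm across six starts at 0.05/6 = 0.0083, where 0.35 vs 0.05 with 10 men per cluster has about 79.8% power in place of 81.6%.

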1 PROTOCOL SUMMARY

1.1 SYNOPSIS

Title:	MASLIHAT Intervention for Tajik Male Migrants Who Inject Drugs
Grant Number:	1R01DA050464
Study Description:	
This protocol will test the efficacy of the MASLIHAT peer education HIV prevention intervention for Tajik migrant laborers who inject drugs in the host country, against an attention control. The primary outcomes are self-reported risk behaviors among participants and network members over 12 months following the intervention, including syringe sharing, and sex without condom. Follow-up interviews will be conducted at 3, 6, 9, and 12 months. We will conduct HIV testing at baseline and 12-month follow-up, and HCV testing at baseline and 6- and 12-month follow-up. We expect the MASLIHAT intervention to be associated with greater reduction in injection and sexual risk behavior during follow-up compared with the control condition.

Objectives[*]:	
Primary Objective: Assess the efficacy of the MASLIHAT intervention compared to the TANSIHAT control condition for reducing injection equipment sharing, condomless sex, and heavy alcohol use among intervention participants and among their network members.
 
Secondary Objectives: Assess the efficacy of the MASLIHAT intervention compared to the TANSIHAT control condition for reducing the incidence of HIV and hepatitis C infection among intervention participants and among their network members

Endpoints[*]:	
Primary Endpoint: Reduce the proportion of men sharing syringes or other injection equipment in the past 3 months to 10% or less; reduce the proportion of men engaging in condomless sex in the past 3 months to 10% or less. Reduce the proportion of men engaging in heavy alcohol use in the past 3 months to 10% or less.
 
Secondary Endpoints: Reduce the 12-month incidence of HIV and HCV by 50% compared to the control group.
 
We will enroll a total of 420 male Tajik migrant workers who inject drugs in Moscow, including 140 intervention participants (70 MASLIHAT, 70 control group) and 280 network members recruited by the intervention participants for participation in the assessments.

Phase[*] or Stage:	Phase 2
Description of Sites/Facilities Enrolling Participants:	Participants will be enrolled at PRIZMA Research Center in Moscow, Russia.

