1.2. HIV risk behavior among Moscow Tajik migrants occurs in a country that has an exceedingly high and still rising HIV rate.²³ While globally new infections declined by an estimated 16% from 2010 to 2017,²⁴ in Eastern Europe and Central Asia the number of new infections grew by an estimated 30%. The Russian Federation accounts for 70% of HIV cases in this region and accounted for 75% of new HIV infections in the region in 2017.¹¹ Most HIV infections in the region are among people who inject drugs (PWID) and their sexual partners,²⁵ yet harm reduction service coverage is low. A recent study of PWID in St. Petersburg reported an HIV incidence rate of 9.3 per 100 person years.²⁶ In the Russian Federation in particular, insufficient access to sterile injecting equipment and the unavailability of opioid substitution therapy (OST) are significant roadblocks to reducing HIV infections among people who inject drugs.^{12, 27} Tajik migrants form a potential bridge for HIV to move from high-prevalence Russia to low prevalence Tajikistan, which currently has a centralized epidemic primarily among PWID. HIV prevalence among PWID in Tajikistan is estimated at 13.5% compared to 25.6% in the Russian Federation.²⁵

1.3. HIV risk behavior among Tajik labor migrants who inject drugs in Russia is alarmingly high. In our first survey of 106 Tajik migrant men who inject drugs (MWID),⁷ 105 (99%) of the sample reported using heroin in Tajikistan before relocating to Moscow; 94% reported injecting drugs at least once a week; and 83% reported having shared needles or syringes in the last 30 days. Sharing unclean "works" appears to be a normative practice. As one of our sample participants explained, "We use the same syringe and

needle every time. We share our equipment; we are one circle of friends.” Meanwhile, although knowledge that HIV can spread sexually was well-known (93%), 66% of the MWID that we sampled didn’t know it could be transmitted through unclean needles. One participant who rejects this notion remarked, ““If it is transmitted through sex, then how can there be a link between HIV and drug use? There isn’t any link.” Only 9 participants reported injecting with a non-Tajik (nearly all Russian women). Condom use was low with 74% of the MWID with regular sexual partners reporting never using them even when buying sex. Risky alcohol consumption was common, with 23% engaging in possible hazardous use according to the WHO Alcohol Use Disorders Identification Test.²⁸

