1.11.(b). Development and pilot test of MASLIHAT (R21DA039068, [name]/[name], PI). In this study we developed, manualized, and pilot tested the MASLIHAT intervention. We presented the proposed intervention to community leaders and solicited their input, and then pre-tested the intervention with a small group of participants and conducted focus groups to collect feedback. After finalizing the intervention manual and assessment instruments, and training facilitators, we pilot tested the intervention with 30 participants who were trained as peer educators (PEs). Prior to the training, each participant recruited two network members to participate in the assessments. Assessments were conducted with the 30 participants and 60 network members at baseline, and 6 weeks, 3 months, and 6 months after the index participant completed the peer educator training. We also collected qualitative feedback from PEs after the training. Nearly all PEs completed the entire sequence of five MASLIHAT sessions; three participants each missed one session, and two participants were removed from a session due to intoxication. There was no loss to follow-up among PEs, and 95% of network members had complete follow-up. Three network members had left Moscow.

We tested the effects of time and participant type on each outcome using GEE and mixed effects regression. HIV knowledge increased significantly from baseline to 6-weeks for both PEs and network members ($B=4.84$, 95% CI 4.15-5.54), with significant reductions in frequent alcohol use (31% to 2.3%), casual sex without a condom (33% to 1%), and syringe sharing (52% to 0%). Neither group reported consistently cleaning their syringes at baseline, but all did sometimes at 6 weeks, and 87% always at 6 months. PEs reported a high level of satisfaction with the sessions delivered by facilitators, and felt that the content was culturally relevant for Tajik migrants who inject drugs.

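### The stated 80% alcohol power belongs to a slope test on past-month drinking days; no power is given for the declared endpoint, the proportion drinking heavily in the past 3 months

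*Combined protocol and SAP*

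**What the plan says.** The alcohol part of Section 9.2 starts from the pilot: "in the pilot study, days of alcohol use in the past month decreased from 5 to 2", "yielding a Cohen's d effect size of -0.69". It then uses "Mixed Models Tests for the Slope Difference in a 3-Level Hierarchical Design with Fixed Slopes (Level-3 Randomization", with subject ICC 0.30, alpha 0.01 and 10, 20 or 30 subjects per cluster. It reports at least 80% power at SMD 0.70 (index men), 0.50 (network members) and 0.41 (complete sample).

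The alcohol endpoint in Section 1.1, repeated in Section 3 under the primary objective, is "Reduce the proportion of men engaging in heavy alcohol use in the past 3 months to 10% or less".

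Sections 6.1.1 and 8.1 name only syringe sharing and condomless sex as primary outcome measures and place the AUDIT among other measures. Drinking days in the past month is not listed. The hypotheses in 9.1 and the primary analysis in 9.4.2 do not mention alcohol. No section gives a cut-off for heavy use.

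The two-proportion routine in 9.2 (ICC 0.05, alpha 0.01, control rates 0.30 to 0.50) is described for condomless sex and syringe sharing only.

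**The concern.** The powered variable and the declared endpoint differ in measure (drinking days against heavy use), scale (continuous against binary), recall window (one month against three) and test (slope difference against a proportion). The 80% therefore does not carry over to the endpoint. Cutting a continuous measure at a threshold usually loses information, and a proportion's power also depends on its base rate, which 9.2 does not state for alcohol.

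A reader of 9.2 would take it that heavy drinking is adequately powered in all three populations. If that comparison then came out null, the stated 80% would invite reading the result as evidence against MASLIHAT, when the plan contains no calculation to support that reading.

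**Working it through.** **Inputs.** Six sites per arm (6.3: 12 sites in matched pairs). k = 10, 20, 30 men per site (9.2), so n = 60, 120, 180 per arm. Alpha 0.01, taken as two-sided because 9.4.1 promises "exact p-values for 2-tailed tests"; z = 2.576. Four equally spaced visits is my inference. Base rates: 31% frequent use at pilot baseline (2.2, item 1.11(b)), "23% engaging in possible hazardous use" on the AUDIT (2.2, item 1.3), and 25% hazardous drinking on the AUDIT-C (2.2, item 1.11(a)). None of these is heavy use as the endpoint words it.

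**1. The plan's own figure.** With unit-spaced visits the time sum of squares is 2.25 + 0.25 + 0.25 + 2.25 = 5. The slope difference is SMD/3, its SE is √[2(1 − 0.30)/(5n)], and power = Φ(slope/SE − 2.576).

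| Group | SMD/3 | SE | Ratio | Power |
|---|---|---|---|---|
| Index | 0.2333 | 0.0683 | 3.416 | 79.95% |
| Network | 0.1667 | 0.0483 | 3.450 | 80.9% |
| Complete | 0.1367 | 0.0394 | 3.465 | 81.3% |

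The printed 80% reproduces. Five visits would give 85–86%, also consistent with *at least 80%*.

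**2. The declared proportion against the 10% target, with 9.2's binary inputs.** Effective n per arm = 6k/[1 + (k − 1)0.05], that is 60/1.45 = 41.4, 120/1.95 = 61.5 and 180/2.45 = 73.5. For a single visit with unpooled variance, power = Φ(|p0 − p1|/√[(p0q0 + p1q1)/n_eff] − 2.576), where q = 1 − p. Example, index men, 31% against 10%: √[(0.2139 + 0.09)/41.4] = 0.0857; 0.21/0.0857 = 2.451; Φ(−0.125) = 45%.

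| Control rate | Index | Network | Complete |
|---|---|---|---|
| 23% | 17% | 27% | 34% |
| 25% | 23% | 37% | 45% |
| 31% | 45% | 66% | 76% |

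**3. The stated SMDs converted to proportions.** Assume a normal latent scale: p1 = Φ(Φ⁻¹(p0) − SMD). From 31% this gives 11.6%, 16.0% and 18.3%.

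- Test of step 2 (ICC 0.05): about 18–36% across groups and base rates.
- Slope formula of step 1 with p0q0 + p1q1 in place of the 2, no site variance: 42/46/48% from 31%, and 34–48% overall.
- Mean of four visits, n_eff = 6/[s + (0.30 − s)/k + 0.70/(4k)], where s is the site ICC and the subject ICC of 0.30 is carried over: 82–94% with s = 0, and about 25–58% with s = 0.05.

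**4. The pilot fall.** If the pilot's change in frequent use (31% to 2.3%) recurred against an unchanged control, one visit with ICC 0.05 (pooled and unpooled variance) gives 84–89% for index men and 97% or more for the other groups. Starting from 23–25%, index power is about 61–73%.

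**The case against.** The strongest reply is that no single low figure can be pinned on the declared endpoint. That stands. Step 3 alone runs from 18% to 94%, depending on the test and the site variance. The planned binary analysis in 9.4.2 is a repeated-measures modified Poisson model, not a single-visit test or a linear slope. It may recover power from the four visits: step 3's averaging formula with s = 0.05 gives n_eff = 64.9, 84.2 and 93.5, and 31% against 10% then has about 69%, 82% and 87%.

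A reader might infer that power is roughly half of what is claimed, or that a shortfall appears even with no site variance. The documents do not support either as a general statement. The 34–48% needs a latent-normal cut, proxy base rates and a slope formula applied to binary data, and averaging four visits with no site variance gives 82–94%.

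A reader might also infer that the trial could not have detected the stated effect. That is too strong. The SMDs of 0.50 and 0.41 are detectable values, while the pilot effect is 0.69 (6.52/√90 = 0.687 if all 90 pilot men are pooled). At 0.69 the binary slope formula with no site variance gives 67–77% for network members and 87–93% for the complete sample, though only 33–41% for index men. With ICC 0.05 and a single visit, the first two fall to 44–54% and 53–64%. The pilot's binary fall would give 84% or more from 31%. Against that, it is an uncontrolled before-and-after change in frequent use, and Section 4.2 says the control programme also addresses heavy alcohol use, so an unchanged control is doubtful.

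Section 4.2 does disclose that this will affect the ability to detect drinking effects. It gives no figure, and 9.2 is not qualified accordingly.

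Finally, alcohol may not be meant as primary: 6.1.1, 8.1 and 9.1 leave it out. That does not rescue the power statement. It adds a second matter to reconcile.

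**Conclusion.** The mismatch holds on the documents alone: 9.2 gives alcohol power for a variable, scale, recall window and test that are not those of the endpoint in Sections 1.1 and 3, and no power is given for that endpoint. There is no arithmetic slip; 80/81/81% is right for the test described, given four equally spaced visits, six sites per arm and two-sided alpha 0.01.

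The size is conditional. Under 9.2's own binary inputs, one visit and the 10% target, all nine combinations of group and control rate in step 2 fall below 80%. That rests on site ICC 0.05, unpooled variance and proxy base rates. The 23% and 25% rates also lie outside the 0.30 to 0.50 control range that 9.2 examined. Power reaches 80% or more if site variance is negligible and visits are averaged, if averaging is combined with a 31% base rate and the two larger groups, or if the pilot fall recurs in full from 31%. The supportable conclusion is that at least 80% power is not shown for the declared endpoint, and that it fails under several of the plan's own inputs.

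**What to change.** 1. Reconcile alcohol's status: primary in Sections 1.1 and 3, absent from the primary lists in 6.1.1 and 8.1 and from the hypotheses in 9.1. Define heavy use by a stated instrument and cut-off.

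2. In 9.2, take one of two routes.
   - Replace the alcohol sentences with two-proportion power for the declared endpoint, at ICC 0.05, alpha 0.01 and control rates of 23–31%, printed as a conditional range. Revise the rates once the cut-off is fixed.
   - Or declare the continuous AUDIT score, already collected at each time point, as the alcohol outcome. Analyse it with the linear mixed model in 9.4.1, restate the detectable SMDs for that score, and keep the 10% proportion as descriptive.

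The cost is protocol and SAP wording plus one rerun of the power routine. The downside is a less favourable stated power, or a relabelled endpoint. No added participants or data are needed.
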